9.3 STATISTICAL METHODS TO BE UNDERTAKEN

Quantitative data analysis:

Clinically significant fatigue will be defined as a mean FSS > 5 (Krupp et al., 1989). Anxiety and depression will be defined as higher HADS (Zigmond & Snaith, 1983). The UWSE will be assessed as a continuous term and dichotomised at the median as there is no established cut off point indicating sufficient self-efficacy.

Characteristics of quality of life (QoL) will be measured by the MSQOL-54, including physical and mental health composite scores and multiple subdomains. Linear regression will be used to determine cross-sectional and prospective relationships with QoL. Characteristics of disability will be assessed using linear regression. Characteristics of dichotomous clinically significant fatigue, depression and anxiety will be assessed by log-binomial regression. Characteristics of Self-efficacy composite scores will be assessed by linear and log-binomial regression for continuous and dichotomised self-efficacy, respectively. Characteristics of perceived social support scores will be

assessed by linear regression. All models will be assessed for potential confounders and appropriate adjustments will be made in analyses.

Qualitative data analysis:

Audio recordings will be transcribed for analysis and stored within Nvivo Software (www.qsrinternational.com) to enable data management. Data analysis will be conducted within a qualitative paradigm using reflexive thematic analysis (Braun 2014). Reflexive thematic analysis is considered the most appropriate analytic process due its lack of grounding in a particular philosophy (Braun 2006), and as a method suitable to exploring people's experiences, views and perceptions (Braun 2014) and its allowing expression of results in a way accessible to those in the wider community. Reflexive thematic analysis also emphasises the importance of the researcher being deeply involved in the research. Data will be analysed by the process of data familiarisation, coding, and theme development and refining. Data extracts (quotes) will illustrate themes.

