	
educational course and completing self-reported questionnaires and possibly two semi-structured qualitative interviews.
 
Any potentially psychological risks from participating in the study have been addressed by contingency plans to provide links to Online help resources and the contact details of study team members to provide further information for participants.

Statistical Methods:	
Analysis of outcomes:
 
Characteristics of quality of life (QoL) will be measured by the MSQOL-54, including physical and mental health composite scores and multiple subdomains. Linear regression will be used to determine cross-sectional and prospective relationships with QoL. Characteristics of disability will be assessed using linear regression. Characteristics of dichotomous clinically significant fatigue and depression will be assessed by log-binomial regression. Characteristics of self-efficacy composite scores will be assessed by linear and log-binomial regression for continuous and dichotomised self-efficacy, respectively. All models will be assessed for potential clinical and demographic confounders and appropriate adjustments will be made in analyses.

Subgroups:	Not applicable
Consumer Involvement	
Consumers have been involved in the co-design of the MSOC RCT. A consumer advisory group comprising of 6-8 people with MS in a series of focus groups was involved in the co-design of the MS Online intervention and standard-care course. The devised course was then tested in a feasibility study (MSOC – Feasibility) involving a subgroup of people with MS (n = 31) and the quantitative and qualitative outcomes of the MSOC – Feasibility study were used to co-design the MS Online intervention and standard-care courses in the proposed RCT.

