The Hospital Anxiety and Depression Scale (HADS) for the presence of and severity of anxiety and depressive symptoms. The HADS is commonly used for screening for anxiety and depression, as well as selecting and monitoring treatment and has been used to measure depression in MS (Zigmond & Snaith, 1983).

i. Patient-reported disability

The Patient-Determined Disease Steps (PDDS) is a self-reported measure of ambulatory disability. The PDDS is scored ordinally from 0 (normal) to 8 (bed bound) with detailed descriptors and definitions. It correlates well with the EDSS and moderately with the widely used Multiple Sclerosis Functional Composite and has excellent test-retest reliability. PDDS is considered a practical tool to use to assess changes in disability over time (Hohol, Orav, & Weiner, 1999). One step will be considered a clinically meaningful change in the PDDS.

j. Self-efficacy

Self-efficacy (the belief in one's ability to produce the effects or outcomes one wants) will be measured using the University of Washington Self-Efficacy (UWSE) survey, a psychometrically sound instrument that includes 6 items for measuring self-efficacy, validated in MS (Amtmann et al., 2012).

Primary intervention quantitative outcomes/endpoints:

The two primary outcome measures for this study are changes (improvements) from baseline in 1. Physical Health Composite (PHC) and 2. Mental Health Composite (MHC) derived from the MSQOL-54 in the short-term and medium-term. Differences of at least five points have previously been determined as the minimum clinically meaningful change in an HRQOL measure (Osoba, Rodrigues, Myles, Zee, & Pater, 1998; Taphoorn & Bottomley, 2005). Previous data suggests a difference of five points is achievable in a sample of people with MS (Hadgkiss, Jelinek, Taylor, et al., 2015).

Secondary intervention quantitative outcomes/endpoints:

Secondary outcomes include clinically relevant changes (improvements) in depression, anxiety fatigue, disability and self-efficacy in the short-term and medium-term.

QUALITATIVE OUTCOMES

A qualitative study using semi-structured interviews will be conducted within one month and 12 months after completing the MS Online course (the same group of people with MS will be interviewed at both time points).

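### Depression and anxiety are analysed only as dichotomised HADS, with no stated cut-off and no analysis of the subscale scores; the synopsis methods paragraph gives anxiety no model

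*Combined protocol and SAP*

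**What the plan says.** Section 9.3 gives HADS one defining sentence: "Anxiety and depression will be defined as higher HADS", followed by a literature citation. The model is then: "Characteristics of dichotomous clinically significant fatigue, depression and anxiety will be assessed by log-binomial regression". No linear or other model of the HADS score appears in 9.3 or in the synopsis.

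Section 5.3 introduces the instrument: "The Hospital Anxiety and Depression Scale (HADS) for the presence of and severity of anxiety and depressive symptoms". It gives no cut-off and no meaningful change, whereas it gives a meaningful change of 1.9 points for the FSS and one step for the PDDS. The endpoint is worded as: "Secondary outcomes include clinically relevant changes (improvements) in depression, anxiety fatigue, disability and self-efficacy in the short-term and medium-term".

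Other outcomes in 9.3 are handled differently. For self-efficacy, "The UWSE will be assessed as a continuous term and dichotomised at the median", with the reason for the median split given. Disability and perceived social support go to linear regression. Fatigue is dichotomised only, but at a stated number (mean FSS above 5).

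The synopsis Secondary Objectives name anxiety. The synopsis Statistical Methods paragraph reads "Characteristics of dichotomous clinically significant fatigue and depression will be assessed by log-binomial regression" and assigns anxiety no model.

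**The concern.** A log-binomial model needs an event that every participant either has or does not have. A word meaning only that the score is higher does not supply one. Two analysts working from this text could define depression differently and both be following the plan.

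The plan also uses HADS only as a status. Section 5.3 says the scale measures severity as well as presence, but the stated analysis drops severity. A participant whose score moves several points without crossing the line contributes nothing to the arm comparison.

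At stake are the precision of two of the five secondary outcomes and confidence that their event definition was not influenced by the results. Analyses are staged (short-term, then 2.5 years), and 6.1 makes a decision about standard-care access depend on 12-month results by arm. A cut-off still open at that stage could be settled with outcome data in hand.

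**Working it through.** **1. Is there a cut-off or a score model anywhere?** The places that deal with HADS are the synopsis, 5.3, Table 1 (14 items, at baseline and all three follow-ups), 8.1 (distress resources) and 9.3. None gives a threshold. None gives a model of the score.

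**2. How many are analysed?** The documents state no power for HADS, so there is no plan figure to reproduce for it. The nearest is the primary sample size in 9.1: 527 per arm, 80% power, 5 points, Bonferroni over two outcomes, 42% loss. The SD is not stated. With an assumed SD of 20 and two-sided 0.025:

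n = 2(SD/Δ)²(z₀.₉₈₇₅ + z₀.₈₀)² = 2(20/5)²(2.241 + 0.842)² ≈ 304.2, so 305 per arm; 305/0.58 ≈ 526, against 527 stated.

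This shows consistency and not reproduction, because an SD of 22 at 0.05 gives 525. It supports reading 527 as the number randomised, with 527 × 0.58 ≈ 306 per arm analysed. The wording of 9.1 also allows 527 per arm with data, and it calls 42% probably too high. Both numbers are used below.

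**3. Power on the score.** Assumptions: normal score, arm difference d = 0.25 SD, two-sided 5%. Power = Φ(d√(n/2) − 1.96).

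- n = 306: Φ(3.092 − 1.96) = 87%
- n = 527: Φ(4.058 − 1.96) = 98%

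**4. Power after dichotomising the same score.** If a proportion p₀ of controls exceed the cut-off, the intervention proportion is p₁ = Φ(z(p₀) − 0.25). With p̄ the mean of the two,

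Power = Φ{[(p₀ − p₁) − 1.96√(2p̄(1 − p̄)/n)] / √([p₀(1 − p₀) + p₁(1 − p₁)]/n)}.

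Information kept, relative to the score, is φ(z(p₀))²/[p₀(1 − p₀)].

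| Control event rate p₀ | p₁ | Information kept | Power, 306 per arm | Power, 527 per arm |
|---|---|---|---|---|
| 15% | 9.9% | 43% | 48% | 71% |
| 30% | 21.9% | 58% | 62% | 85% |
| 50% | 40.1% | 64% | 69% | 90% |
| Score itself | – | 100% | 87% | 98% |

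**5. Does the normal assumption drive this?** A simulation used a skewed integer score from 0 to 21, with assumed SD 3.8, control means of 5, 6.5 and 8, d = 0.227, 306 per arm and 5,000 runs. The score had about 81% power throughout. A cut at 6 or more gave 64% to 81%, at 8 or more 37% to 67%, and at 11 or more 14% to 38%. With the lowest cut and the highest mean the loss is essentially nil. With the highest cut, power is below half that of the score. These cuts were chosen only to show sensitivity.

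**The case against.** **The cut-off may be implied by the citation.** Section 9.3 justifies the median split for self-efficacy by the lack of an established threshold and gives no such reason for HADS. That suggests the authors had a published cut-off in mind. This is fair: a reader might infer that any threshold at all would be allowed, and the text does not go that far. The number is still not stated, and a citation alone does not fix it.

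**Selection is guarded against.** Section 6.3 blinds research staff, including those doing the statistical analyses, and the Data Analysis section lists a statistical analysis plan still to be developed. Both reduce the risk. They do not remove it: nothing says the cut-off will be fixed before follow-up data are analysed, 9.1 expects unblinding at 12 months, and the present text directs any later plan to a binary model.

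**A clinical state is a legitimate endpoint.** The secondary outcomes are worded as clinically relevant changes, and fatigue too is only dichotomised, so HADS is not the lone exception. That stands. It is a reason to keep a binary analysis, but not to make it the only one.

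**No stated power is lost.** The trial claims power only for PHC and MHC. With 527 per arm, two of the three illustrated binary cases still exceed 80%. A reader might infer that much of the power for depression and anxiety is certainly lost; the documents give no HADS SD, event rate, effect or cut-off, so they cannot support that.

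**Two further inferences fail.** It is tempting to say that the synopsis omits anxiety altogether; only its Statistical Methods paragraph does. It is also tempting to say that participants below the line at baseline contribute nothing; when follow-up status is compared between arms, they contribute through new cases.

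**Conclusion.** The point holds in this form: depression and anxiety are analysed solely as dichotomous outcomes, the event has no stated cut-off, the subscale scores are not analysed, and the synopsis methods paragraph leaves anxiety without a model. These are matters of text and rest on no assumption.

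That dichotomising discards information is general; how much it costs here is illustrative. Under a normal score and a 0.25 SD difference, the fall in power is 18 to 39 percentage points with 306 per arm (87% to between 69% and 48%) and 8 to 27 points with 527 (98% to between 90% and 71%). A low cut on a skewed score can make it small. Because the loss varies so much with the cut-off, the cut-off should not be left open.

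The change should be made but is not critical: these are secondary outcomes, and the primary analyses of PHC and MHC are unaffected.

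**What to change.** In 9.3 and the synopsis Statistical Methods paragraph:

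1. Make the main HADS analysis a linear regression of the HADS-Depression score and, separately, the HADS-Anxiety score on arm at each follow-up, with the baseline subscale score as covariate.
2. Replace the present defining sentence with one numeric cut-off per subscale, fixed before any follow-up data are analysed. Keep the log-binomial analysis on that cut-off as supportive, so that the clinically relevant wording in 5.3 is still addressed.
3. Add anxiety to the synopsis model list, to agree with 9.3 and with the synopsis Secondary Objectives.

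The cost is a few sentences and a little more analysis work. HADS is already collected at baseline and every follow-up, so nothing is added for participants. The downside is that the main HADS result becomes a mean score difference and not a risk ratio, which some readers find harder to interpret; the supportive analysis supplies the ratio.

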Primary Objectives:	
To determine whether participants adhering to lifestyle modification recommendations outlined in the MS Online intervention course have clinically significant increased health-related quality of life (HRQOL) in both domains of physical and mental health compared with participants following recommendations of the MS Online standard-care course. These outcomes will be examined in the short-term (6 and 12 months) and in the medium-term (2.5 years).
 
That is, we aim to determine whether participants in the Online intervention course following recommended lifestyle modifications have clinically significant and material increases in Physical Health Composite (PHC) and Mental Health Composite (MHC) scores, as derived from the validated tool designed to measure HRQOL in people with MS (MSQOL-54) compared with participants following recommendations of the Online standard-care course.

Secondary Objectives	
To determine whether participants following the lifestyle modification recommendations in the Online MS intervention course have improved depression, anxiety, fatigue, disability and self-efficacy in the short-term and medium-term compared with people following recommendations of the Online MS standard-care course.

Inclusion Criteria:	
Eligible participants must:
 
 1. Be able to read, write, and speak English; 2. Be 18 years old or over; 3. Have a confirmed diagnosis of relapsing-remitting MS by a neurologist preceding recruitment; 4. Be able to access the internet and be able to view sessions.
Exclusion Criteria:	
Exclusion criteria of participants include:
 
 1. Experiencing any serious co-morbid chronic illness or neurological illness/injury other than MS that would threaten regular participation or significantly affect the outcome measures in its own right, such as motor neurone disease or stroke, as determined by the study investigators; 2. Currently participating in another study or self-management program involving modification of lifestyle.
Number of Planned Participants:	
1054 participants, 527 in each arm at 1:1 allocation (intervention and standard-care arm)

Investigational product:	
Not applicable

Safety considerations:	
Participation in the study poses no physical risk to participants as the proposed RCT involves taking part in an Online MS

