The 12-item multidimensional Scale of Perceived Social Support (MSPSS) will be used to measure participants' social interaction and satisfaction with social support (Zimet, Dahlem, Zimet, & Farley, 1988). Higher score of MSPSS indicates higher quality of social support.

Health outcomes of participants will be assessed at baseline and 6, 12 and 30 months after completion of the respective Online MS course. Health outcomes measured include:

f. Mental and physical quality of life (qol)

The MSQOL-54 will be used to assess a spectrum of HRQOL outcomes. In particular, the two primary outcome measures for this study will be change in Physical Health Composite (PHC) and Mental Health Composite (MHC) derived from the MSQOL-54. PHC and MHC are derived by combining scores of relevant subscales (Vickrey, Hays, Harooni, Myers, & Ellison, 1995). Although minimal clinically important differences have not been established for the MSQOL-54 composite scores, differences of at least five points have previously been determined as the minimum clinically meaningful change in an HRQOL measure (Osoba et al., 1998; Taphoorn, et al., 2005). This is based on recommendations that a difference

equivalent to half the standard deviation be universally considered an important magnitude for all HRQOL tools (Norman, Sloan, & Wyrwich, 2003). The MSQOL-54 has been psychometrically validated since 1995, used online and also translated into many different languages.

g. Fatigue

Clinically significant fatigue will be measured by the 9-item Fatigue Severity Scale (FSS) (Krupp, LaRocca, Muir-Nash, & Steinberg, 1989). The FSS has good internal consistency, stability, and sensitivity to change over time (Amato et al., 2001; Smedal et al., 2011). A mean score ≥ 4 has been suggested as a cut-off to indicate clinically significant fatigue and is widely used for people with MS (Lerdal, Celius, & Moum, 2003; Marrie et al., 2005; Smedal et al., 2011). A meaningful change on the FSS has been reported demonstrated to be a change of ≥ 1.9 points in people with MS (Learmonth et al., 2013) and so here a change in mean score of 1.9 points or more will be considered clinically meaningful.

h. Anxiety and depression

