9. STATISTICAL METHODS

9.1 SAMPLE SIZE ESTIMATION & JUSTIFICATION

The two primary outcome measures for this study are changes in Physical Health Composite (PHC) and Mental Health Composite (MHC) derived from the MSQOL-54. PHC and MHC are derived by combining scores of relevant subscales (Vickrey et al., 1995). For the proposed MSOC – RCT, sample sizes were calculated in order to detect a 5-point difference in the PHC and MHC scores (a minimum clinically meaningful change in these HRQOL measures, between the intervention and standard-care arms).

To further account for loss-to-follow-up from the study period, based upon MSOC - Feasibility results, we anticipated a 42% loss-to-follow-up between randomisation and follow-up at 12 months. It is likely

this level of loss-to-follow-up is an overestimate of what will be observed in the proposed MSOC – RCT due to redevelopment of the intervention based upon feasibility data, but this overestimate will account for participants in the standard-care course that request access to the MS Online Intervention course after unblinding at 12 months after participants undertake the MS Online Standard-care course.

Taking these factors into account, we estimate 1054 participants, 527 in each arm (1:1 allocation) with data at baseline and follow-up would give 80% power to detect a 5-point change in HRQOL across both PHC and MHC outcomes. This estimation of power is based on the mean PHC and MHC scores and their SD, which is the SD between groups at baseline.

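### Self-efficacy is analysed both as a continuous score and split at an unspecified median, with neither named as the main analysis; the split does not measure the stated endpoint and is less efficient

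*Combined protocol and SAP*

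**What the plan says.** Section 5.3 sets the endpoint: "Secondary outcomes include clinically relevant changes (improvements) in depression, anxiety fatigue, disability and self-efficacy in the short-term and medium-term". It describes the UWSE as "a psychometrically sound instrument that includes 6 items for measuring self-efficacy, validated in MS" but gives no threshold for a meaningful change. For two other secondary scales it does give one: 1.9 points on the FSS and one step on the PDDS.

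Section 9.3 sets the analysis: "The UWSE will be assessed as a continuous term and dichotomised at the median". The same sentence goes on to give the reason for the median, the score being "dichotomised at the median as there is no established cut off point indicating sufficient self-efficacy". The models follow: "Characteristics of Self-efficacy composite scores will be assessed by linear and log-binomial regression for continuous and dichotomised self-efficacy, respectively". The statistical methods entry in the synopsis lists the same two models without naming the cut.

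On timing, section 5.3 says: "Health outcomes of participants will be assessed at baseline and 6, 12 and 30 months after completion of the respective Online MS course". Nothing states whether the median is taken at baseline or at follow-up, over both arms or within each, or once or at every survey. Nothing says which of the two analyses decides the self-efficacy result.

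**The concern.** The binary outcome and the endpoint do not match. Being above a sample median says where a person ranks among the responders. It does not say whether that person improved, or whether any improvement matters clinically. Section 9.3 concedes that no cut-off on this scale carries such a meaning, yet it gives the split its own regression model on equal footing with the continuous score.

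Two analyses at three follow-up surveys give six results for one secondary outcome, with no rule if they disagree. A risk ratio for high self-efficacy may also be read as a clinical statement that it cannot support. The unspecified median adds a further risk, because one possible reading would distort each arm's apparent change from baseline.

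**Working it through.** The plan gives no figure for self-efficacy, so there is none to reproduce.

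**Inputs**
- Randomised per arm: 527 (section 9.1).
- Loss by 12 months: 42% (section 9.1). Responders per arm: 527 × (1 − 0.42) = 305.7, taken as 306.
- UWSE distribution: not given. Assumed normal with equal SD in both arms; shifts are in SD units and the baseline median is 0.
- Test: two-sided 0.05 (assumed, since no level is stated for secondary outcomes), without baseline adjustment.

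**Step 1. Power for a 0.3 SD difference (gains of 0.3 and 0)**

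Continuous score: SE = √(2/306) = 0.0808. Then 0.3/0.0808 − 1.96 = 1.75, so power is Φ(1.75) = 96%.

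Split at the pooled follow-up median (0.15): the shares above it are Φ(0.15) = 56.0% and Φ(−0.15) = 44.0%, a difference of 0.119. The null SE is √(2 × 0.25/306) = 0.0404 and the alternative SE is √(2 × 0.560 × 0.440/306) = 0.0401. Then (0.119 − 1.96 × 0.0404)/0.0401 ≈ 1.00, so power is 84%.

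Split at a fixed baseline median (0): the shares are Φ(0.3) = 61.8% and 50.0%, a difference of 0.118. The SEs are 0.0401 and 0.0399. Then (0.118 − 1.96 × 0.0401)/0.0399 ≈ 0.98, so power is again 84%.

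The loss therefore comes from splitting and hardly depends on which pooled median is used. The same formulas give:

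| Responders per arm | Difference | Continuous | Split, follow-up median | Split, baseline median |
|---|---|---|---|---|
| 306 | 0.3 SD | 96% | 84% | 84% |
| 306 | 0.2 SD | 70% | 50% | 50% |
| 527 (no loss) | 0.3 SD | 99.8% | 97% | 97% |
| 527 (no loss) | 0.2 SD | 90% | 74% | 73% |

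For small differences, the efficiency of a median split relative to the continuous score is 2/π = 64%.

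**Step 2. What each reading of the median would show**

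With gains of a (intervention) and b (standard care), the pooled follow-up median is m = (a + b)/2. The shares above it are Φ(a − m) and Φ(b − m). With the cut fixed at baseline they are Φ(a) and Φ(b). Each arm starts at 50%.

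| Gain: intervention / standard care | Median recomputed at follow-up | Median fixed at baseline |
|---|---|---|
| 0.5 / 0.5 SD | 50.0% / 50.0% | 69.1% / 69.1% |
| 0.7 / 0.5 SD | 54.0% / 46.0% (RR 1.17) | 75.8% / 69.1% (RR 1.10) |
| 0.2 / 0.5 SD | 44.0% / 56.0% (RR 0.79) | 57.9% / 69.1% (RR 0.84) |

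Under the recomputed cut a common gain disappears, and the arm that gained less seems to fall (50% to 46.0% in the second row, 50% to 44.0% in the third) although its scores rose. Under the fixed cut neither happens. In every row the two cuts agree on which arm did better.

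**The case against.** A reader might infer that the cut moves with the sample at each survey, so that the endpoint cannot show improvement. The documents do not support that. Section 9.3 says only that the split is at the median, and a single baseline median fits the words equally well; under that reading the distortion in step 2 does not arise. The same sentence keeps the continuous score with its own linear model, where improvement can be shown.

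A reader might also infer that the comparison of arms could come out reversed. It could not under a pooled median. The secondary objective is a between-arm one: whether participants "have improved depression, anxiety, fatigue, disability and self-efficacy in the short-term and medium-term compared with people following recommendations of the Online MS standard-care course". That contrast keeps its direction under either pooled cut, with nearly equal power. With equal gains, 50% against 50% is the correct null result. Section 9.3 plans no within-arm analysis of the dichotomised score. Medians taken separately within each arm would remove the contrast, but nothing in the text suggests this.

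The defence can add that self-efficacy is one of five secondary outcomes, that the plan is open about the missing cut-off, and that a statistical analysis plan is listed as a later task under Data Analysis, where the median could be specified.

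All of this stands, and it confines the point to the dichotomised analysis. It does not answer the rest. Specifying the median would still leave a binary outcome that measures neither change nor clinical relevance, at lower power, and unranked against the better analysis.

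**Conclusion.** The point holds in a limited form. The median split is a stated inferential analysis of equal standing with the continuous score. It does not measure the endpoint defined in section 5.3, and it lowers power for a 0.3 SD difference from about 96% to 84% with 306 per arm (from about 70% to 50% for 0.2 SD). These figures rest on normal scores, equal SDs, a two-sided 0.05 test and the planned 42% loss, which section 9.1 calls a likely overestimate. With less loss the gap at 0.3 SD narrows.

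The hidden common gain and the apparent decline are conditional on a median recomputed at each survey, which the plan does not state. They concern an arm's own change from baseline in the binary version only. The primary outcomes are unaffected. This is a cheap improvement to one secondary analysis and does not threaten the trial's conclusions.

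**What to change.** In section 9.3 and the synopsis, make the continuous UWSE score, adjusted for its baseline value, the single inferential self-efficacy analysis, and remove the log-binomial model for the dichotomised score. If a proportion is wanted for presentation, fix the cut once at the pooled baseline median of all randomised participants, apply it unchanged at 6, 12 and 30 months, state how scores equal to the cut are classed, and label the result descriptive.

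This takes a sentence in each place and one analysis fewer. The baseline and follow-up scores are already collected. The downside is that there is no inferential risk ratio for self-efficacy. The change also does not supply a threshold for clinically relevant UWSE change, so the result should be reported as a mean difference with its confidence interval.

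### The plan names one PDDS step as the meaningful change in disability, but its only disability analysis, a linear regression with no stated outcome form or baseline term, never uses that threshold

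*Combined protocol and SAP*

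**What the plan says.** Section 5.3, under patient-reported disability, states: "The PDDS is scored ordinally from 0 (normal) to 8 (bed bound) with detailed descriptors and definitions". It then sets the threshold: "One step will be considered a clinically meaningful change in the PDDS". The secondary endpoints in the same section are framed in terms of clinical relevance: "Secondary outcomes include clinically relevant changes (improvements) in depression, anxiety fatigue, disability and self-efficacy in the short-term and medium-term".

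The synopsis words the secondary objective more plainly. It asks whether intervention participants "have improved depression, anxiety, fatigue, disability and self-efficacy in the short-term and medium-term compared with people" in the standard-care arm, with no clinical-relevance qualifier.

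The analysis is one sentence in section 9.3, which also appears in the synopsis: "Characteristics of disability will be assessed using linear regression". It does not say whether the outcome is the follow-up score or the change from baseline, whether baseline PDDS enters the model, or which time point leads. Section 9.3 adds that all models will be assessed for confounders and adjusted as appropriate, without naming baseline PDDS.

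The other secondary outcomes each have a categorical analysis: "Characteristics of dichotomous clinically significant fatigue, depression and anxiety will be assessed by log-binomial regression". Self-efficacy has both a linear and a log-binomial model. Disability has an explicit meaningful-change threshold but no categorical analysis.

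**The concern.** The endpoint is phrased as clinically relevant improvement and the threshold is one step, yet no planned analysis counts who reaches it. A difference in means combines people who got better with people who avoided getting worse, so it cannot show how many participants improved by a step. The entry criteria set no PDDS limit, so people at PDDS 0 can enrol. They can worsen but cannot improve, and the plan has no rule for presenting them.

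Two things are at stake. The disability result could be statistically significant without any pre-specified statement about the plan's own criterion. And because the outcome form and baseline term are open, power for this outcome depends on a choice not yet made.

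**Working it through.** **Inputs.** From section 9.1: 527 per arm and 42% loss by 12 months, so 527 × (1 − 0.42) = 305.7, taken as 306 per arm. From section 5.3: PDDS 0 to 8, threshold one step. The documents give no PDDS baseline distribution, SD or target effect, so there is no plan figure to reproduce. Every PDDS figure below is an assumption, tested at two-sided 5%.

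**Step 1: one mean difference, two different results.** Let change be +2, +1, 0, −1, −2 steps, with positive meaning better.

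| Arm | Percent at +2, +1, 0, −1, −2 | Mean | SD | Improved ≥1 | Worsened ≥1 |
|---|---|---|---|---|---|
| Control | 2, 13, 60, 20, 5 | −0.13 | 0.770 | 15% | 25% |
| Intervention, case A | 2, 28, 45, 20, 5 | 0.02 | 0.872 | 30% | 25% |
| Intervention, case B | 2, 13, 70, 15, 0 | 0.02 | 0.600 | 15% | 15% |

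Both cases differ from control by 0.02 − (−0.13) = 0.15 step. Power of the mean comparison is Φ(0.15 / (s√(2/306)) − 1.96), where s² is the average of the two variances.

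- Case A: s = 0.823, 0.15/0.0665 = 2.26, power 62%.
- Case B: s = 0.690, 0.15/0.0558 = 2.69, power 77%.

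Comparing improvers in case A, 30% against 15%: pooled 0.225, SE = √(2 × 0.225 × 0.775/306) = 0.0338, 0.15/0.0338 = 4.44, power 99%. In case B there is no difference in improvers to detect. The linear coefficient is the same in both.

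**Step 2: size of a detectable mean difference.** The difference with 80% power is (1.96 + 0.84) × SD × √(2/306). For an assumed SD of 0.75 to 1.5 this is 0.17 to 0.34 step. Differences of 0.12 to 0.24 step (1.96 × SD × √(2/306)) would reach p < 0.05. If all 527 per arm gave follow-up data, the 80%-power range would be 0.13 to 0.26. A significant result may therefore be a fraction of a step.

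**Step 3: the floor.** If a share f starts at PDDS 0, at most 1 − f can improve. For f = 20%, 35% or 50% that is 80%, 65% or 50%. An arm-mean improvement of one step would need an average of 1/(1 − f) = 1.25, 1.54 or 2.0 steps in the rest, even if nobody at 0 worsened. In simulation with those floors and no effect, baseline-adjusted linear regression rejected in 5.0–5.7% of trials, so the test of means keeps about its nominal size.

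**Step 4: power of the candidate analyses.** Assumed: 40% at PDDS 0, 20% at 1, the rest spread over 2 to 8; latent baseline-to-follow-up correlation 0.7 or 0.85; odds ratio 0.70 for a worse category; 306 per arm. The mean difference is about 0.31–0.32 step. Improvers are 36% against 30% (correlation 0.7) or 34% against 25% (0.85). Ranges span repeated simulations and, for the last row, the formula below.

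| Analysis | Correlation 0.7 | Correlation 0.85 |
|---|---|---|
| Linear, follow-up score, no baseline | 59–62% | 57–60% |
| Linear, change score | 72–74% | 92–93% |
| Linear, follow-up score with baseline | 81–84% | 95% |
| Proportional odds with baseline | 80–88% | 93–96% |
| Improvers by ≥1 step, unadjusted | 35–45% | 66–69% |

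Formula check on the last row. For 36% against 30%: SE = √(2 × 0.33 × 0.67/306) = 0.0380, 0.06/0.0380 = 1.58, Φ(1.58 − 1.96) = 35%. For 34% against 25%: SE = 0.0369, 0.09/0.0369 = 2.44, Φ(0.48) = about 69%.

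**The case against.** Four points can fairly be made for the plan.

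- **The coefficient is in PDDS steps.** A reader might infer that linear regression is invalid here, or that its result cannot be set against one step. The documents do not support either. Section 5.3 does not say whether one step applies within a person or between arm means, and section 9.1 uses the analogous 5-point threshold for the quality-of-life composites as a between-arm difference. Test size is about nominal, and the synopsis objective asks only for improved disability. This stands in full.
- **The gap is one of specification.** A reader might infer that one-step change will never be compared, or that the model will be unadjusted. Section 9.3 leaves adjustment open, and the data analysis paragraph at the end of section 12 lists a statistical analysis plan still to be developed. The accurate statement is that neither item is yet specified.
- **An ordinal model is largely a preference.** Setting an unadjusted linear model against an adjusted ordinal one would credit the ordinal model with what the baseline covariate does. With baseline in both, the ordinal model moved power from 84% to 88% and 95% to 96% in one set of runs, and from 81% to 80% and 95% to 93% in another with sparse top categories merged. The gain is nil to 4 points.
- **Comparing improvers alone can lose power.** On the step 4 assumptions it does. The order depends on the assumptions: if 30% of the intervention arm shifts one step better, with floors of 20%, 35% or 50%, improvers give 99.5%, 98% and 93.5% against 97%, 95% and 89.5% for the adjusted mean. This supports reporting both.

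The inputs are also open to challenge. The step 4 model has 30% or 25% of controls improving by a step, which sits awkwardly with the high test-retest reliability that section 5.3 attributes to the PDDS.

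None of this supplies an analysis that uses the one-step threshold.

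**Conclusion.** The point holds in a limited form. The planned linear regression is a valid comparison of means and answers the synopsis objective. It does not estimate the clinically relevant improvement named in section 5.3, and its outcome form and baseline term are missing. On assumed distributions, one mean difference of 0.15 step is compatible with a difference in one-step improvers of 0 or 15 percentage points. On the step 4 assumptions, pre-specifying baseline PDDS is worth roughly 20 to 40 points of power over an unadjusted follow-up score, and about 2 to 12 over a change score.

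These sizes rest on assumed PDDS distributions, correlations and effects. The share of participants at PDDS 0 is unknown, so the weight of the floor cannot be stated. Disability is one of several secondary outcomes; the sample size and the primary analysis do not depend on it.

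**What to change.** In section 9.3 and the synopsis:

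1. Model follow-up PDDS on arm, with baseline PDDS as a pre-specified covariate, and state that the dependent variable is the follow-up score.
2. At 6 months, 12 months and 2.5 years, report by arm the proportions improved, unchanged and worsened by at least one step, with the between-arm difference and its confidence interval. Show improvement also among those with baseline PDDS of 1 or more.
3. Optionally, add a proportional-odds model with baseline PDDS as a sensitivity analysis, checking the proportional-odds assumption and merging sparse upper categories.

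The one-step proportions supplement the adjusted mean model and do not replace it, since the improver comparison alone may have as little as 35–69% power on the step 4 assumptions. The cost is wording and standard models: Table 1 already schedules the PDDS at baseline and every follow-up.
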